4.2 Scientific Rationale for Study Design

4.2.1 Rationale for Study Blinding

Given the different appearance of the *C. difficile* investigational vaccines and placebo, double blinding is not possible, and the study will be conducted in an observer-blind manner. In an observer-blind study, the subject, the Contract Research Organization personnel, and the study center and Sponsor personnel involved in the clinical evaluation of the subjects are blinded while other study personnel may be aware of the treatment assignment.

When all data up to Day 61 are available, a statistical analysis will be performed (first interim analysis). The immunogenicity data available until Day 61, and the safety and reactogenicity data available at the time of this analysis will be described. At this point, the statistician will be unblinded for the analysis (ie, will have access to individual subject treatment assignments). The remaining study personnel will stay blinded (ie, will not have access to the individual subject treatment assignment) until study end. It is possible however, due to the limited sample size, that unblinding occurs for a few subjects having a specific adverse event (AE) or serious adverse event (SAE) (eg, an AE/SAE occurring only in a single group). Therefore, anyone having access to the analysis of Day 61 could become unblinded regarding those specific cases. The study will be considered as partial blind from this point onwards.

The third dose will be administered to the Step 4 subjects who received the active components, in a partial blind manner. The Investigator and the subjects will not have access to the treatment allocation up to study end (Day 390). After Day 390, only the subjects will remain fully blinded, while the Investigator will be partially blinded, as no placebo subjects will be included for Dose 3.

Please refer to [Appendix 2](#) for the definition of observer-blind and partial blind.

4.2.2 Rationale for Randomization and the Use of Placebo

Randomized, placebo-controlled studies are widely considered to be the most rigorous method for the efficacy evaluation of treatments or prevention interventions. To be ethical, clinical

research requires balancing rigorous science with the protection of subjects. The use of placebo controls in studies for conditions with no effective treatment is widely accepted.⁶ Up to date, there is no established standard of care to prevent CDI.

Likewise, the Declaration of Helsinki allows placebo controls and states: “Where for compelling and scientifically sound methodological reasons the use of placebo is necessary to determine the efficacy or safety of an intervention and the patients who receive placebo will not be subjected to additional risks of serious or irreversible harm.”⁷

Randomization is used to reduce bias of selection and the placebo group is included as a control for the reactogenicity, the safety and the immunogenicity assessments.

The third dose of the vaccine is being given to the subjects recruited in the active groups of the last step of the study, to demonstrate if a similar kinetics in terms of anti-Toxin A/Toxin B can be achieved with the F2 antigen formulation with or without an adjuvant. Therefore, the third dose will not be given to the subjects receiving placebo.

4.2.3 Rationale for the Use of F2 Fusion Protein Antigen

The F2 antigen is a fusion protein comprising the C-terminal portions of Toxin A and Toxin B. The rationale for selecting the C-terminal portions of Toxin A and Toxin B is based on the fact that these portions correspond to the binding domains of the toxins.

Substantial evidences suggest a protective role of antitoxin antibodies. In humans, antibodies against *C. difficile* Toxin A and Toxin B have been reported to protect against CDI^{8,9,10,11} and recurrent episodes of CDI.^{12,13,14} There is evidence suggesting that antibodies to the C-terminal part of Toxin B can drive protection while data remain unclear on the protective role conferred by antibodies induced by the C-terminal part of Toxin A.

4.2.4 Rationale for the Use of AS01_B Adjuvant

As the *C. difficile* investigational vaccine is intended for subjects at risk for CDI who also may have an impaired immune system due to immunosenescence and/or comorbidities, the *C. difficile* investigational vaccine includes an adjuvant. Using an adjuvant might indeed help to induce a higher and longer-lasting immune response.

The *C. difficile* investigational vaccine used in the present study will be adjuvanted with AS01_B. AS01_B is an adjuvant included in the GSK Biologicals’ Herpes Zoster vaccine marketed as *Shingrix*, which has recently received regulatory approvals in the US, Canada, Europe, and Japan for the prevention of shingles in adults aged 50 years and above. AS01_B contains 50 µg of MPL and 50 µg of QS-21 (a saponin molecule purified from the bark extract of *Quillaja saponaria* Molina, fraction 21 [Licensed by GSK from Antigenics Inc. a wholly owned subsidiary of Agenus Inc. a Delaware, USA corporation]).

4.2.5 Rationale for the Safety Monitoring Plan

The *C. difficile* investigational vaccine will be administered for the first time in humans therefore a 4-step staggered design will be used to allow evaluation of safety of the 2 formulations (with or without adjuvant) in a limited number of subjects before exposing a larger number of subjects to the *C. difficile* investigational vaccine (refer to Section 4.1). The *C. difficile* investigational vaccine without adjuvant will be first administered to subjects aged 18-45 years before administration to subjects aged 50-70 years (refer to Section 4.1 and to Figure 1).

The *C. difficile* investigational vaccine without adjuvant will be administered to approximately 55 subjects (approximately 10 subjects aged 18-45 years and approximately 45 subjects aged 50-70 years), the *C. difficile* investigational vaccine with AS01_B adjuvant will be administered to approximately 45 subjects aged 50-70 years and placebo will be administered to approximately 40 subjects (approximately 10 subjects aged 18-45 years and approximately 30 subjects aged 50-70 years) (refer to Section 8.11 for study procedures to be considered during special circumstances).

For Steps 1, 2, and 3 only, vaccination will be limited to a maximum of 10 subjects per day. Subjects will be vaccinated sequentially, separated by a minimum interval of 60 minutes to allow for monitoring of any acute events (eg, hypersensitivity reaction). During all 4 steps, all subjects should be closely observed for at least 60 minutes after vaccination.

Specific holding rules are defined to ensure well-controlled exposure to the *C. difficile* investigational vaccine (see Section 4.6.1).

4.3 Justification for Dose

The F2 candidate antigen developed by GSK contains a portion of the amino acids sequence of the full-length *C. difficile* toxins. Another manufacturer developing a *C. difficile* vaccine based on the use of genetically detoxified full-length Toxin A and Toxin B, reported optimal immunogenicity data at a dose of 100 µg each (clinical trial: NCT01706367). The proposed dose of F2 antigen is defined to obtain an equivalent number of epitopes (included in F2 sequence) as reported in the Phase I study.

Moreover, findings from the repeated dose toxicology study indicate that the investigational vaccine F2/AS01_B was well tolerated when administered three times at two-week intervals. No safety risks were identified. Please refer to the current IB for more information regarding the preclinical studies of *C. difficile* investigational vaccine (GSK2904545A).

In addition to these observations, pooled analyzes of AS01 adjuvanted vaccines in humans yielded that there is no safety concern for the administration of the same AS01 adjuvanted vaccine. Increase of reactogenicity is expected after dose 2 or dose 3 of the same adjuvanted vaccine.

Based on these data, it is recognized that CDIFF F2 AS01_B has an acceptable safety profile (reactogenicity).

4.4 End of Study Definition

See [Appendix 2](#) for the definition of EoS.

Study conclusion for individual subjects: A subject is considered to have completed the study if he/she returns for the concluding visit/is available for the concluding contact (Visit 7 [Day 390] for subjects receiving 2 doses and Visit 11 [Day 670] for subjects receiving 3 doses) as described in the protocol.

Global completion of the study is required in order to provide sufficient subjects as defined in Section [9.2](#).

4.5 Dose Escalation Criteria

Not applicable.

4.6 Study Holding Criteria

4.6.1 Study Holding Rules

The safety holding rules which will be assessed by the Investigator are defined in [Table 11](#) and the safety holding rules which will be assessed by the iSRC are defined in [Table 12](#). The toxicity grading scales for hematology, biochemistry, and urinalysis parameters applicable for this study are presented in [Table 13](#).

Table 11 Holding Rules Assessed by the Investigator

Holding Rule	Event	Number of Subjects
1a	Death or any life-threatening SAE.	≥1
1b	Any withdrawal from the study following a Grade 3 AE that cannot reasonably be attributed to a cause other than vaccination.	≥1
1c	Any SAE or fever >40°C (104°F) that cannot reasonably be attributed to a cause other than vaccination, or visible necrosis at the injection site, within the 7-day (Day 1 to Day 7) period after vaccination.	≥1

AE = adverse event; SAE = serious adverse event.

Table 12 Holding Rules Assessed During Internal Safety Review Committee Evaluations

Holding Rule	Event	Percentage of Subjects
2a	Any Grade 3 solicited local AE (lasting 48 hours or more) in an investigational group, within the 7-day (Day 1 to Day 7) period after vaccination.	≥20% (per group)
2b	Any Grade 3 solicited general AE (lasting 48 hours or more) in an investigational group, that cannot reasonably be attributed to a cause other than vaccination, within the 7-day (Day 1 to Day 7) period after vaccination.	≥20% (per group)
2c	Any Grade 3 unsolicited AE in an investigational group, that cannot reasonably be attributed to a cause other than vaccination, within the 7-day (Day 1 to Day 7) period after vaccination.	≥20% (per group)
2d	Any Grade 3 abnormality in prespecified hematological or biochemical laboratory parameters in an investigational group within the 7-day (Day 1 to Day 7) period after vaccination (refer to Table 13).	≥20% (per group)

AE = adverse event.

[Figure 2](#) illustrates that, with 10 subjects per group:

- For holding rules 1a, 1b, and 1c, using a cutoff of 1/10, there is more than 80% chance that the holding rule is met for a vaccine with a true incidence rate above 15% and there is more than 60% chance that the holding rule is not met for a vaccine with a true incidence rate below 5%.
Since this holding rule will be assessed on a continuous basis by the Investigator, irrespective of the number of subjects enrolled, the statistical interpretation of this holding rule is less relevant.
- For holding rules 2a, 2b, 2c, and 2d, using a cutoff of 2/10, there is more than 80% chance that the holding rule is met for a vaccine with a true incidence rate above 27% and there is more than 80% chance that the holding rule is not met for a vaccine with a true incidence rate below 8%.

A similar figure is presented for 45 subjects per group ([Figure 3](#)).

Figure 2 Evaluations Based on 10 Enrolled Subjects - Risk Assessment Curves for 1 Formulation Based on the Proposed Safety Holding Rules

[figure not shown]

Figure 3 Evaluations Based on 45 Enrolled Subjects - Risk Assessment Curves for 1 Formulation Based on the Proposed Safety Holding Rules

[figure not shown]

Table 13 Toxicity Grading Scales for Hematology, Biochemistry, and Urinalysis Parameters Applicable for this Study

Discipline (System)	Component	CCI - This section contained Clinical Outcome Assessment data collection questionnaires or indices, which are protected by third party copyright laws and therefore have been excluded.
Hematology (whole blood)	Hemoglobin (gm/dL) - female	
	Hemoglobin (gm/dL) - male	
	Hemoglobin (gm/dL) - female change from baseline value	
	Hemoglobin (gm/dL) - male change from baseline value	
	White blood cells increase (cell/mm ³)	
	White blood cells decrease (cell/mm ³)	
	Platelets decrease (cell/mm ³)	
Biochemistry (serum)	Alanine aminotransferase (increase by factor)	
	Aspartate aminotransferase (increase by factor)	
	Creatinine (mg/dL)	
	Uric acid	
Urinalysis (urine)	Protein (mg/dL)	

CTCAE = Common Terminology Criteria for Adverse Events; FDA = Food and Drug Administration; iSRC = internal safety review committee; ULN = upper limit of the normal range

The laboratory values provided in these tables are taken from the FDA Guidance for Industry “Toxicity Grading Scale for Healthy Adults and Adolescent Volunteers Enrolled in Preventive Vaccine Clinical Trials”, except for uric acid for which laboratory values are taken from CTCAE Version 4.^{15,16}

^a In case Grade 3 hematology or biochemistry parameter is observed, a re-testing should be performed if deemed necessary by the Investigator, the iSRC, or the Sponsor.

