Type of contact	Screening ^a	Visit 1	Visit 2	Visit 3	Visit 4	Visit 5	Visit 6	Visit 7	Screening for Dose 3, Step 4	Visit 8 for Step 4	Visit 9 for Step 4	Visit 10 for Step 4	Visit 11 for Step 4
Timepoints	Day -15	Day 1	Day 8	Day 31	Day 38	Day 61	Day 180	Day 390	Day 476	Day 491	Day 498	Day 521	Day 670
Return of paper diary cards			○	○	○	○					○	○	
Diary card transcription by Investigator			●	●	●	●					●	●	
Recording of solicited AE (Day 1 to Day 7)		●	●	●	●					●	●		
Recording of unsolicited AE (Day 1 to Day 30)		●	●	●	●	●				●	●	●	
Recording of SAEs (all, fatal, related to study vaccine)		●	●	●	●	●	●	●	●	●	●	●	●
Recording of SAEs related to study participation, or to a concurrent GSK medication/vaccine	●	●	●	●	●	●	●	●	●	●	●	●	●
Recording of AEs of specific interest (pIMDs)		●	●	●	●	●	●	●	●	●	●	●	●
Recording of pregnancies		●	●	●	●	●	●	●	●	●	●	●	●
Study conclusion for individual subjects								● ^b					● ^m

AE = adverse event; D = Day; ELISA = enzyme-linked immunosorbent assay; eCRF = electronic case report form; GSK = GlaxoSmithKline Biologicals SA; iSRC = internal safety review committee; PBMC = peripheral blood mononuclear cell; pIMD = potential immune-mediated disease; SAE = serious adverse event; TNA = toxin neutralization assay.

Note: The double-line border following Day 61 indicates the analyses which will be performed on all data (ie, data that are as clean as possible) obtained up to Day 61.

- Used to indicate a study procedure that requires documentation in the individual eCRF.

- Used to indicate a study procedure that does not require documentation in the individual eCRF.
- ^a If the Investigator believes there is a reasonable justification to do so, screening procedures may be repeated (maximum 1 rescreening per subject is allowed). Only laboratory results from the Rescreening Visit, if it occurs, will be taken into consideration and recorded in the eCRF. Medical history, physical examination and review of inclusion/exclusion criteria must be repeated if a Rescreening Visit occurs. The subject can only be randomized once the Investigator receives the results and confirms the eligibility criteria.
- ^b Date of birth, sex, and race to be recorded in the subject's eCRF.
- ^c Medical occurrences that begin before the start of study treatment but after obtaining informed consent will be recorded in the subject's eCRF.
- ^d Physical examination, if deemed necessary by the Investigator or delegate.
- ^e To be performed prior to vaccination.

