- ^f A urine pregnancy test will be performed only for women of childbearing potential.
- ^g Contraindications to subsequent vaccinations are detailed in Section 6.2.
- ^h The following hematological (white blood cells, platelets count and hemoglobin) and biochemical (alanine aminotransferase, aspartate aminotransferase, creatinine, and uric acid) parameters will be assessed at all timepoints specified above. C-reactive protein will be assessed only during the *two* screening visits.
- ⁱ In case Grade 3 hematology or biochemistry parameter is observed, a retesting should be performed if deemed necessary by the Investigator, the iSRC, or the Sponsor.
- ^j Optional blood sampling for retesting, if deemed necessary by the Investigator.
- ^k An additional blood sample will be collected from subjects in Step 4 at Visit 5. This sample will be optional. PBMC may be used for the generation of monoclonal antibodies.
- ^l The study conclusion for subjects receiving 2 doses will be on Visit 7.
- ^m The study conclusion for subjects receiving 3 doses will be on Visit 11.

Table 7 Intervals Between Study Visits (Refer to Section 8.11 for Study Procedures to be Considered During Special Circumstances)

Interval	Optimal Length of Interval	Allowed Interval
Screening → Visit 1 (Day 1)	1 to 15 days	-
Visit 1 (Day 1) → Visit 2 (Day 8)	7 days	7 to 9 days
Visit 1 (Day 1) → Visit 3 (Day 31)	30 days	30 to 35 days
Visit 3 (Day 31) → Visit 4 (Day 38)	7 days	7 to 9 days
Visit 3 (Day 31) → Visit 5 (Day 61)	30 days	30 to 35 days

Visit 3 (Day 31) → Visit 6 (Day 180)	149 days	140 to 160 days
Visit 3 (Day 31) → Visit 7 (Day 390)	359 days	350 to 395 days
Visit 7 (Day 390) → Screening Dose 3 (Day 476)	20 to 150 days	-
Screening Dose 3 (Day 476) → Visit 8 (Day 491)	1 to 15 days	-
Visit 8 (Day 491) → Visit 9 (Day 498)	7 days	7 to 9 days
Visit 8 (Day 491) → Visit 10 (Day 521)	30 days	30 to 35 days
Visit 8 (Day 491) → Visit 11 (Day 670)	179 days	170 to 190 days

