3.0 OBJECTIVES AND ENDPOINTS

Table 9 Study Objectives and Endpoints

Objectives	Endpoints

Primary
 
 To evaluate the safety and reactogenicity profile of the C. difficile F2 fusion protein when administered with or without AS01B adjuvant as IM doses according to a 0, 1-month schedule, in healthy adults aged between 18-45 years and between 50-70 years followed by an additional dose administered approximately 15 months after Dose 2 in a subcohort of subjects aged 50-70 years, during the entire study period. 	
 Solicited local and general symptoms. 
 Occurrence of solicited local symptoms (any and Grade 3) within 7 days (Day 1 to Day 7) after each vaccination, in all subjects and in all groups. Occurrence of solicited general symptoms (any, Grade 3, related, and Grade 3 related) within 7 days (Day 1 to Day 7) after each vaccination, in all subjects and in all groups. Unsolicited AEs. 
 Occurrence of unsolicited AEs (any, Grade 3, related, Grade 3 related, and those resulting in a medically attended visit) within 30 days (Day 1 to Day 30) after each vaccination, according to the MedDRA classification, in all subjects and in all groups. SAEs. 
 Occurrence of SAEs from Dose 1 (Day 1) up to study end, in all subjects and in all groups. AEs of specific interest. 
 Occurrence of AEs of specific interest (pIMDs) from Dose 1 up to study end, in all subjects and in all groups. Laboratory parameters 
 Occurrence of hematological (white blood cells, platelets count, and hemoglobin level) and biochemical (alanine aminotransferase, aspartate aminotransferase, creatinine, and uric acid) laboratory abnormalities at Screening, Days 8, 31, 38, 180, 390, 476, 491, 498, and 670 and urinary laboratory abnormalities (protein, glucose, and blood) at Screening. (Grades will be based on the local laboratory normal ranges and derived from the FDA Toxicity Grading Scale for laboratory abnormalities).

Table 9 Study Objectives and Endpoints

Objectives	Endpoints
Secondary	

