A poststudy AE/SAE is defined as any event that occurs outside of the AE/SAE reporting period defined in [Table 17](#). Investigators are not obligated to actively seek AEs or SAEs in former study subjects. However, if the Investigator learns of any SAE, including a death, at any time after a subject has been discharged from the study, and he/she considers the event to be reasonably related to the study vaccine(s), the Investigator will promptly notify the Study Contact for Reporting SAEs.

Refer to [Appendix 6](#) for local (injection site) and general solicited AEs to be collected.

At each vaccination visit, paper diary cards will be provided to the subject. The subject will be instructed to measure and record the oral body temperature, and any solicited local/general AEs (ie, on the day of vaccination and during the next 6 days) or any unsolicited AEs (ie, on the day of vaccination and during the next 30 days) occurring after vaccination. The subject will be instructed to return the completed diary card to the Investigator at the next study visit.

Adverse events of specific interest (AESIs) for safety monitoring include pIMDs (refer to [Appendix 2](#) for definition of pIMD). Adverse events that need to be recorded and reported as pIMDs include those listed in [Table 18](#).

Table 18 List of Potential Immune-mediated Diseases

Neuroinflammatory disorders	Musculoskeletal disorders	Skin disorders

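### Laboratory holding rule 2d looks at Day 1 to Day 7 after a dose, but the first scheduled post-dose safety sample is taken on Day 8 to 10

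*Protocol*

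**What the plan says.** Protocol Section 4.6.1, Table 12, lists four group-level holding rules that the iSRC assesses. Rule 2d is the laboratory one. It counts Grade 3 abnormalities in prespecified haematological or biochemical "laboratory parameters in an investigational group within the 7-day (Day 1 to Day 7) period after vaccination" and is met at 20% or more of a group.

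The text on Figure 2 in the same section gives all four rules one set of operating characteristics: "For holding rules 2a, 2b, 2c, and 2d, using a cutoff of 2/10, there is more than 80% chance" of a hold when the true rate is above 27%, and more than 80% chance of no hold when it is below 8%.

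Three other places fix the timing:

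- Section 8.3.1 describes the solicited diary period as "on the day of vaccination and during the next 6 days".
- Table 7 (Section 1.3) sets the visit intervals. The rows "Visit 1 (Day 1) → Visit 2 (Day 8"), "Visit 3 (Day 31) → Visit 4 (Day 38") and "Visit 8 (Day 491) → Visit 9 (Day 498") each allow 7 to 9 days.
- The laboratory endpoint in Section 3.0 lists "laboratory abnormalities at Screening, Days 8, 31, 38, 180, 390, 476, 491, 498, and 670". Table 6, footnote e, marks the blood draws at Visits 1, 3 and 8 "To be performed prior to vaccination". At Visit 1 the safety draw is only an optional retest (footnote j).

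**The concern.** Rules 2a to 2c concern events that subjects can report day by day in the first week, so a Day 1 to Day 7 window suits them. A laboratory abnormality is known only from a blood sample and is dated by it. If no planned sample falls inside the window, the rule has nothing to count.

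Rule 2d is the only group-level laboratory trigger in a first-in-human study that uses it to decide whether to give the second dose and open the next step. A rule that planned data cannot meet gives no prespecified protection, and the operating characteristics stated for it would mislead anyone relying on them.

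**Working it through.** **1. The plan's own figure.** For 10 subjects and a cutoff of 2, with X binomial(10, p):

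- P(X ≥ 2) = 1 − (1 − p)^10 − 10p(1 − p)^9.
- At p = 0.27: 1 − 0.73^10 − 2.7 × 0.73^9 = 0.798. The probability reaches 80% at p = 0.271, so the stated 27% is right after rounding.
- At p = 0.08, P(X < 2) = 0.92^10 + 0.8 × 0.92^9 = 0.812, as stated.

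The characteristics are therefore correct for an event that the rule can observe.

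**2. Day count.** With the vaccination day as Day 1, a sample taken k days after the dose falls on post-dose Day k + 1. Section 8.3.1 uses this count, SAP Section 6.4 uses the same one for study day, and Protocol Table 17 shows D7 and D8 as separate columns. Day 7 is k = 6.

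**3. Scheduled haematology and biochemistry samples, by dose** (intervals from Table 7):

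| Preceding dose | Visit | Days after dose | Post-dose day | Inside Day 1–7? |
|---|---|---|---|---|
| 1 | 2 | 7–9 | 8–10 | No |
| 1 | 3 (before Dose 2) | 30–35 | 31–36 | No |
| 2 | 4 | 7–9 | 8–10 | No |
| 2 | 6 | 140–160 | 141–161 | No |
| 2 | 7 | 350–395 | 351–396 | No |
| 2 (Dose 3 subcohort) | Dose 3 screening; 8 (before Dose 3) | later than Visit 7 | later than Visit 7 | No |
| 3 | 9 | 7–9 | 8–10 | No |
| 3 | 11 | 170–190 | 171–191 | No |

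That is 0 of 5 samples for a two-dose subject and 0 of 9 for a three-dose subject. Only Visits 2, 4 and 9 could reasonably serve a first-week rule, and the earliest of them misses the window by one day. The blood drawn at Visits 3 and 8 precedes the dose given that day, so it is not a sample after that vaccination even though it carries the same date.

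**4. Sensitivity to the day count.** If the vaccination day were Day 0, contrary to the protocol, a visit exactly 7 days after the dose would fall on Day 7 and count. Visits at 8 or 9 days, which are equally allowed, still would not.

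**5. Effect on the rule.** The table gives the chance that rule 2d is met. The 8% and 27% rates are the protocol's; 30% is an illustrative rate.

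| True Grade 3 rate | As written, scheduled samples only | First post-dose sample counted, 2 of 10 | First post-dose sample counted, 9 of 45 |
|---|---|---|---|
| 8% | 0% | 18.8% | 0.8% |
| 27% | 0% | 79.8% | 89.3% |
| 30% | 0% | 85.1% | 95.3% |

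The cutoff for 45 subjects is 0.20 × 45 = 9.

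**The case against.** The strongest reply is that this is a window copied from rules 2a to 2c, and that nobody meant to ignore the Day 8 sample. Visits 2 and 4 close out the first week, and Table 6, footnote i, lets the iSRC ask for a retest of a Grade 3 value, so the committee was clearly expected to look at these results. That intent is likely. It does not change what the rule says, because a laboratory value has no onset date other than its sample date.

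The second reply is that the same action is available by another route. Under Section 9.7 the iSRC reviews all accumulating safety data and may hold for a signal outside the listed rules, with the same consequence. The next dose needs a written favourable outcome (Sections 4.1 and 6.1), and a Grade 3 value bars that individual from further doses (Section 6.2). This stands: detection and the power to hold are intact, and the 0% above is not the chance that the study is held. But none of these carries a group threshold. Rule 2c does not fill the gap either, since its window is the same and an abnormality first found on Day 8 and recorded as an adverse event from that date would fall outside it.

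Two limits also stand. An unscheduled sample on Day 1 to 7, which Section 8.0 permits, could count. After Dose 3 only an ad hoc iSRC meeting is foreseen, so rewording the rule would not by itself cause it to be assessed at Visit 9. The rationale for Amendment 03 already reports interim two-dose results with an acceptable safety profile, so for Doses 1 and 2 much of the benefit is now retrospective.

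**Conclusion.** The concern holds. As written, no scheduled safety sample after any of the three doses falls inside the rule 2d window, and the operating characteristics claimed for the rule do not apply to it: 0% from scheduled samples, against about 80% at a 27% true rate with 10 subjects. This rests on the protocol's own convention that the vaccination day is Day 1, on visits taking place within the Table 7 intervals, and on counting scheduled samples only.

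The practical harm is limited by the iSRC's discretion and by the individual contraindication. The iSRC charter is not among the documents, so how the committee treats Day 8 results in practice is unknown. If it counts them, it departs from the written rule; if it does not, planned data cannot trigger the rule. Either way the text should be corrected. No endpoint, analysis or sample size is affected.

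**What to change.** In Table 12, replace the rule 2d window with: *at the first scheduled post-dose safety visit (Visit 2, 4 or 9) or in any earlier unscheduled sample*. Use the same wording in the iSRC charter.

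A window of Day 1 to Day 10 would work equally well when visits are on time. Tying the rule to the visit is safer, because Section 8.11 lets blood-sampling intervals be extended in special circumstances. The Section 4.6.1 statement on rules 2a to 2d then holds for 2d and can stay.

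The cost is one line in Table 12 and matching charter wording, with no new visit, sample or procedure. For doses already reviewed, the study report should say whether the Visit 2 and Visit 4 results were counted towards rule 2d.
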